2.2.2 Secondary Endpoints

- Proportion of subjects with each grade of adverse events as defined by CTCAE v4.03 will be computed along with 95% confidence intervals, and reported in a tabular and descriptive manner.
- Median PFS times will be computed, and PFS rate at 1 year +/- 3 months will be calculated with associated 95% confidence intervals based on the Kaplan-Meier method. Median OS times will be computed, and OS rate at 1 year +/- 3 months will be calculated with associated 95% confidence intervals based on the Kaplan-Meier method.

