6. TOXICITIES AND DOSE DELAYS/DOSE MODIFICATIONS

The NCI Common Terminology Criteria for Adverse Events (CTCAE) v4.03 will be used to grade adverse events.

Subjects enrolled in this study will be evaluated clinically and with standard laboratory tests before and at regular intervals during their participation in this study as specified in Study Calendar & Evaluations.

Subjects will be evaluated for adverse events (all grades), serious adverse events, and adverse events requiring study drug interruption or discontinuation as specified in Study Calendar & Evaluations.

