7. STUDY CALENDAR & EVALUATIONS

Study Evaluations Cycle = 21 days for Pembrolizumab Cycle = 5 days for HD IL-2	Screening	Cycles 1-2 Pembrolizumab (P)	End of Cycle 2 Pembro	Cycle 1 HD IL2	Cycle 2 HD IL2	Safety follow up visit ¹¹	Long-term Follow up ¹²
	-28 days	Day 1 (± 3 days)	Day 21 (± 3 days)	Days 1-5	Days 15-19	28 days post last dose (± 7 days)	Every 3 months (±14 days)
REQUIRED ASSESSMENTS							
Informed Consent/HIPPA authorization	X						
Medical History ¹	X						
Diagnosis and Staging ²							
Physical Exam	X	X	X	X	X	X	
Vital signs and ECOG Performance Status ³	X	X	X	X	X	X	
AEs & concomitant medications	X	X	X	X	X	X	
LABORATORY ASSESSMENTS							
Complete Blood Cell Count with diff (CBC)	X	X ¹⁰	X	X	X	X	
Comprehensive Metabolic Profile (CMP)	X	X ¹⁰	X	X	X	X	
PT/INR and aPTT	X	X ¹⁰					
Thyroid Function (TSH, T4, free T3)	X		X				
Vitamin D level	X						
Pregnancy test (serum or urine) (WOCBP) ⁴	X	X ⁴					
Urinalysis	X	X ¹⁰	X		X		
DISEASE ASSESSMENT							
Chest X-ray				X			
CT of chest ⁵	X		X			X	
CT or MRI of abdomen and pelvis ⁵	X		X			X	
CT or MRI Brain ⁵	X		X			X	
TREATMENT EXPOSURE							
Pembrolizumab		X					
HD IL-2				X	X		
SPECIMEN COLLECTION							
Archival Tumor Tissue ⁶	X						
Blood Samples ⁷		X ⁷	X	X	X ⁷		
Stool sample ⁸		X					

Study Evaluations Cycle = 21 days for Pembrolizumab Cycle = 5 days for HD IL-2	Screening	Cycles 1-2 Pembrolizumab (P)	End of Cycle 2 Pembro	Cycle 1 HD IL2	Cycle 2 HD IL2	Safety follow up visit ¹¹	Long-term Follow up ¹²
	-28 days	Day 1 (± 3 days)	Day 21 (± 3 days)	Days 1-5	Days 15-19	28 days post last dose (± 7 days)	Every 3 months (±14 days)
BANKING SAMPLES							
Whole blood, Plasma and PBMCs ⁹		X ⁹	X			X	
FOLLOW-UP							
Survival Status, Subsequent Therapy							X

Key to Footnotes

CBC with differential and platelet to include: Hgb, Hct, WBC, ANC, lymphocyte count, platelets. CMP to include sodium, potassium, chloride, creatinine, blood urea nitrogen; liver function tests (LFTs) to include AST, ALT, total bilirubin, alkaline phosphatase

1: Medical History to include documentation of prior anti-cancer treatment including medications (chemotherapy, checkpoint inhibitors, etc.), radiation, or surgery. A question of how the subject learned about the study will be asked.

2: Diagnosis and staging to include pathology report and Tumor Node Metastasis (TNM) staging.

3: Vital signs to include blood pressure, weight, and height (screening only) and ECOG performance status.

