10.2.6 Side Effects

Please refer to the current version of the Investigator's Brochure for a complete list of adverse events.

The following adverse events (Grades 1-4) were seen in $\geq 30\%$ of 525 patients (255 with metastatic renal cell cancer and 270 with metastatic melanoma) treated with Proleukin®: hypotension (71%), diarrhea (67%), oliguria (63%), chills (52%), vomiting (50%), dyspnea (43%), rash (42%), bilirubinemia (40%), thrombocytopenia (37%), nausea (35%), confusion (34%), and creatinine increase (33%). Due to the potential severe adverse events that might accompany Proleukin therapy at the recommended dosages, thorough clinical evaluation will be performed to exclude subjects that are contraindicated to Proleukin therapy and patients that have significant cardiac, pulmonary, renal, hepatic, or CNS impairment. Adverse events are frequent, often serious, and sometimes fatal. Further details around frequency, reporting, and management of immune-related adverse events (irAEs) can be found in the current version of the Investigator's Brochure. In addition to the previously noted identified risks, infusion-related reactions are a risk but are not considered immune mediated; these are also further described in the current IB.

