11.1 Definitions

11.1.1 Adverse Event (AE)

An AE is any untoward medical occurrence whether or not considered related to the study drug that appears to change in intensity during the course of the study. The following are examples of AEs:

- Unintended or unfavorable sign or symptom
- A disease temporally associated with participation in the protocol
- An intercurrent illness or injury that impairs the well-being of the subject

Abnormal laboratory values or diagnostic test results constitute AEs only if they induce clinical signs or symptoms or require treatment or further diagnostic tests

Hospitalization for elective surgery or routine clinical procedures that are not the result of an AE (e.g., surgical insertion of central line) should not be recorded as an AE.

Disease progression should not be recorded as an AE, unless it is attributable to the study regimen by the site investigator.

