11.2 Reporting

11.2.1 Adverse Events

- AEs will be recorded from time of signed informed consent until 30 days after discontinuation of HD IL-2.
- AEs will be recorded regardless of whether or not they are considered related to the pembrolizumab or HD IL-2.
- All AEs will be recorded in the subject's medical record and on the appropriate study specific eCRF form within the EDC system.
- Asymptomatic laboratory abnormalities that do not require treatment will not be collected as adverse events.

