12.2.2 Secondary Endpoints

To characterize safety, tolerability and adverse effects (AE) profile of pembrolizumab followed by HD IL-2 in subjects with stage IV malignant melanoma. Proportion of subjects with each grade of adverse events as defined by CTCAE v4.03 will be computed along with 95% confidence intervals, and reported in a tabular and descriptive manner.

To measure Progression-Free Survival (PFS) using revised RECIST 1.1 after completion of 2 cycles of pembrolizumab and 2 cycles of HD IL-2 in all the subjects enrolled in the study. Median PFS times will be computed if reached, and PFS rates at 1 year +/- 3 months will be calculated with associated 95% confidence intervals based on the Kaplan-Meier method.

To measure overall survival (OS) at 12 months in subjects with stage IV malignant melanoma who showed a response [stable disease (SD), complete response (CR) or partial response (PR)] following completion of 2 cycles of pembrolizumab and 2 cycles of HD IL-2. Median OS times will be computed, and OS rate at 1 year +/- 3 months will be calculated with associated 95% confidence intervals based on the Kaplan-Meier method.

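### Safety is reported by CTCAE grade, but asymptomatic untreated laboratory abnormalities are not collected as AEs and no laboratory-grade table is planned

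*Combined protocol and SAP*

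**What the plan says.** **Endpoint.** Section 2.2.2 reads "Proportion of subjects with each grade of adverse events as defined by CTCAE v4.03 will be computed along with 95% confidence intervals", and Section 12.2.2 repeats it. Safety is the first secondary objective (Section 2.1.2). Section 6 sets the scope: "Subjects will be evaluated for adverse events (all grades), serious adverse events, and adverse events requiring study drug interruption or discontinuation".

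**Collection rule.** Section 11.2.1: "Asymptomatic laboratory abnormalities that do not require treatment will not be collected as adverse events". It makes no exception by grade.

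**Definition.** Section 11.1.1: "Abnormal laboratory values or diagnostic test results constitute AEs only if they induce clinical signs or symptoms or require treatment or further diagnostic tests".

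**Known HD IL-2 laboratory toxicity.** Among events seen in at least 30% of 525 patients (Grades 1-4), Section 10.2.6 lists "bilirubinemia (40%), thrombocytopenia (37%), nausea (35%), confusion (34%), and creatinine increase (33" percent). Three of these five (bilirubin, platelets, creatinine) are laboratory findings.

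**Data available.** The Section 7 calendar schedules CBC and CMP at screening, on Day 1 of the pembrolizumab cycles, at the end of pembrolizumab, in both HD IL-2 cycles and at the safety visit. Its key includes ANC, platelets, creatinine, total bilirubin, AST and ALT. Section 14.1 commits only selected data to the EDC. No section plans a table of laboratory grades.

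**The concern.** The safety table is built from AE records, and the collection rule removes some laboratory abnormalities before they become AE records. A reader who sees rates by CTCAE grade will naturally take them as the frequency of low platelets or raised bilirubin or creatinine. They will be the frequency of the subset that caused symptoms or was treated.

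Two features make this more than a labelling question:

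- Under Section 6.2.1, low ANC or platelets hold back an HD IL-2 cycle and lead to weekly repeat blood work, with or without symptoms or treatment. Such a count can delay therapy and still go uncollected under Section 11.2.1, although Section 6 says that events requiring interruption are evaluated.
- Sections 11.1.1 and 11.2.1 draw the line in different places, so two sites could record the same abnormality differently.

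At stake is how complete the first secondary objective will be, and the AE summary that goes to the DSMB (Section 13.2). The primary endpoint is not involved.

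**Working it through.** **1. The plan's own figure.** The plan gives no safety calculation. The only design figure is the Simon design that sets N = 29 (Section 12.3: stop at 3 or fewer of 11, reject at 11 or fewer of 29). Exact binomial calculation gives an early-termination probability of 0.6854 at P = 0.26 (plan: 0.685), one-sided alpha of 0.0429 and power of 0.8075 at P = 0.50. It reproduces, and nothing below changes it.

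**2. The two rules side by side.**

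| Laboratory abnormality | AE under 11.1.1? | Collected under 11.2.1? |
|---|---|---|
| Causes signs or symptoms | Yes | Yes |
| Asymptomatic, requires treatment | Yes | Yes |
| Asymptomatic, untreated, requires further diagnostic tests | Yes | No |
| Asymptomatic, untreated, no further tests | No | No |

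The third row is a contradiction. The weekly repeat counts in Section 6.2.1 could arguably fall in it. The fourth row is excluded by both rules. So the AE count for a laboratory toxicity is at most the count graded from the laboratory values, and no planned analysis recovers the difference. The direction is certain; the size is not.

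**3. Expected counts if everything were collected.** Inputs: the rates in Section 10.2.6, assumed to apply here, and N = 29, all assumed to receive HD IL-2.

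- Bilirubinemia: 29 × 0.40 = 11.6
- Thrombocytopenia: 29 × 0.37 = 10.7
- Creatinine increase: 29 × 0.33 = 9.6

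**4. Reported rates under the rule.** Let s be the share that is asymptomatic and untreated. The documents do not give s, so it is an assumption. Reported rate = listed rate × (1 − s); expected count = 29 × reported rate.

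| s | Bilirubinemia | Thrombocytopenia | Creatinine increase |
|---|---|---|---|
| 0% | 40% (11.6) | 37% (10.7) | 33% (9.6) |
| 10% | 36% (10.4) | 33.3% (9.7) | 29.7% (8.6) |
| 25% | 30% (8.7) | 27.8% (8.0) | 24.8% (7.2) |
| 50% | 20% (5.8) | 18.5% (5.4) | 16.5% (4.8) |
| 75% | 10% (2.9) | 9.3% (2.7) | 8.3% (2.4) |

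**5. Chance that at least one affected subject is missed.** This is 1 − (1 − rate × s)^29. At s = 10%, thrombocytopenia gives 1 − (1 − 0.037)^29 = 0.665; bilirubinemia gives 0.694 and creatinine increase 0.622. At s = 25% the three range from 0.918 to 0.953.

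**6. What the confidence interval shows.** Section 12.2.2 names no interval method for AEs; I used the exact binomial that Section 12.2.1 names for response. For thrombocytopenia, with counts rounded to whole subjects:

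- Full collection, 11/29: 20.7% to 57.7%
- s = 25%, 8/29: 12.7% to 47.2%
- s = 50%, 5/29: 5.8% to 35.8%

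The interval describes sampling error around the collected rate. It carries no information about what was not collected.

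**The case against.** The strongest reply is that the endpoint counts adverse events, the protocol defines that term in Section 11.1.1, and CTCAE is adopted to grade events that meet the definition. On that reading the endpoint is fully computable and the collection rule is a deliberate, common convention. This stands. A reader might infer that the endpoint cannot be computed for laboratory toxicities; the documents do not support that.

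Four further points also stand:

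- **Grade.** Abnormalities that cause symptoms or are treated are still collected, so losses should fall mainly on lower grades. For immune-related hepatic and renal events, Table 2 in Section 6.1.3 already directs corticosteroids from Grade 2, so those would be collected. The gap is mainly in the HD IL-2 phase.
- **Prominence.** The three toxicities rank 8th, 9th and 12th of the 12 listed in Section 10.2.6. They are frequent, but they do not lead the list.
- **Denominator.** Subjects who progress stop protocol therapy (Section 6.2, Protocol Therapy Discontinuation) but stay in the safety set after one dose (Section 12.4), so not all 29 need receive HD IL-2. The trial may also stop after 11 subjects.
- **Comparison with Section 10.2.6.** A reader might infer that this trial's rates would look better than the listed IL-2 rates only because of how they were collected. Section 10.2.6 does not say how its rates were ascertained, and the plan specifies no such comparison. That bias is possible but not shown.

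The reply does not remove the direction of the under-reporting, the missing laboratory table, or the disagreement between Sections 11.1.1 and 11.2.1. Section 14.2 lets selected standard-of-care data into the EDC, so a laboratory table is not precluded, but nothing commits the trial to one.

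**Conclusion.** The concern holds as a cheap improvement. The planned table will be valid for AEs as the protocol defines them, and it will equal or understate laboratory-defined toxicity of HD IL-2, including low counts that delay a cycle. The size cannot be found from the documents. The illustration (about 30% to 10%, 28% to 9% and 25% to 8% reported, against 40%, 37% and 33%) rests on three assumptions: the Section 10.2.6 rates apply, all 29 subjects receive HD IL-2, and 25% to 75% of these toxicities are asymptomatic and untreated. If that share is zero, nothing is lost.

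A reader might also take the two AE sections together to mean that an untreated, asymptomatic value can never become an AE. Section 11.1.1 does not say so, because it admits values that require further diagnostic tests. That disagreement with Section 11.2.1 is a separate defect and does not depend on any assumed share.

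**What to change.** 1. Keep an AE convention for laboratory values, but reconcile Sections 11.1.1 and 11.2.1 so that both treat abnormalities needing further diagnostic tests in the same way, and say whether repeat counts under Section 6.2.1 are such tests.
2. Add to Section 12.2.2: *Worst post-baseline CTCAE v4.03 grade will be derived from all available CBC and CMP values, scheduled and unscheduled, and tabulated with 95% CIs alongside the AE table.* Unscheduled values matter because the weekly repeats under Section 6.2.1 lie outside the calendar and could hold the worst grade.
3. Confirm that these values are entered in the EDC, since Section 14.1 commits only selected data.

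The scheduled CBC and CMP are already drawn under Section 7, so no test or visit is added for the subject. The cost is one derived table and some data entry, larger if inpatient or unscheduled values are not yet captured. The primary endpoint, sample size, alpha and power do not change.

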11.2.2 Serious Adverse Events (SAEs)

11.2.2.1 Site Requirements for Reporting SAEs to HCRN

- SAEs will be reported from time of signed informed consent until 30 days after discontinuation of HD IL-2.
- SAEs will be reported on the SAE Submission Form **within 1 business day** of discovery of the event.
- SAEs include events related and unrelated to pembrolizumab or HD IL-2.
- All SAEs will be recorded in the subject's medical record and on the appropriate study specific eCRF form within the EDC system.

The site will submit the completed SAE Submission Form to HCRN **within 1 business day** of discovery of the event. The form may be submitted to HCRN electronically to [contact]. The site investigator is responsible for informing the IRB and/or other local regulatory bodies as per local requirements.

The original copy of the SAE Submission Form and the email correspondence must be kept within the study file at the study site.

Once the SAE has resolved (see resolution guidelines listed above), sites must submit a follow-up SAE Submission Form within a reasonable timeframe to HCRN electronically to [contact].

11.2.2.2 HCRN Requirements for Reporting SAEs to Prometheus

HCRN will report all SAEs to Prometheus as stipulated by each company (i.e., all SAEs, only those related etc.) **within 1 business day** of receipt of the SAE Submission Form from a site. Follow-up information will be provided to Prometheus as it is received from site.

Contact information for Prometheus

Drug Safety Email: [contact]

Drug Safety [contact]

11.3 Sponsor-Investigator Responsibilities

HCRN will send a SAE summary to the sponsor-investigator **within 1 business day** of receipt of SAE Submission Form from a site. The sponsor-investigator will promptly review the SAE summary and assess for expectedness and relatedness.

11.4 HCRN Responsibilities to FDA

HCRN will continue to facilitate compliance of applicable requirements for the sponsor-investigator in relation to this study. This includes but is not limited to 21 CFR 50.20 informed consent, 21 CFR Part 56 IRB, and pertinent sections of the Public Health Service Act and FDAAA.

11.5 IND Safety Reports Unrelated to this Trial

Prometheus will provide to HCRN IND safety reports from external studies that involve the study drug(s) per their guidelines. HCRN will forward safety reports to the sponsor-investigator who will review these reports and determine if revisions are needed to the protocol or consent. HCRN will forward these reports to participating sites **within 1 business day** of receiving the sponsor-investigator's review. Based on the sponsor-investigator's review, applicable changes will be made to the protocol and informed consent document (if required). All IND safety reports will also be made available to sites via the EDC system. Upon receipt from HCRN, site investigators (or designees) are responsible for submitting these safety reports to their respective IRBs, as per their IRB policies.

12 STATISTICAL METHODS

12.1 Study Design

The primary objective of this single arm Phase II trial is to assess the response rate [complete response (CR) + partial response (PR)] of sequential therapy of pembrolizumab followed by HD IL-2 in subjects with stage IV malignant melanoma. Response assessment will be performed using revised RECIST guideline (version 1.1). The trial will consist of two phases. In the first phase of this trial, therapy will be initiated with pembrolizumab followed by HD IL-2 therapy. Pembrolizumab 200 mg will be given every 3 weeks for 2 doses (cycles). Staging will occur approximately 20 days after the last treatment dose (i.e., Day 21 [+3 days] of Cycle 2). Then subjects will receive HD IL-2 for 2 cycles, Cycle 2 separated from Cycle 1 by 9 days (one course). Subjects are hospitalized during each cycle which consists of up to 14 infusions over a 5 day period (3 infusions/day spaced 8 hours apart). Four weeks after the last HD IL-2 administration of Cycle 2, the subjects will be restaged (i.e., their disease status reassessed). For subjects with progressive disease as revealed by the restaging, they will be followed for OS up to one year from initiation of the first treatment (pembrolizumab) of the study. For subjects with CR, PR, and SD, scans will be performed at 3-month intervals until disease progression or up to a year after initiation of the first treatment (with pembrolizumab) on study. For the subjects who progress, although they will be taken off the study they will be followed for OS up to one year from initiation of the first treatment (pembrolizumab) of the study.

12.2 Endpoints and Analyses

12.2.1 Primary Endpoint

The primary endpoint of this single arm Phase II trial is to assess the response rate [complete response (CR) + partial response (PR)] of sequential therapy of pembrolizumab followed by HD IL-2 in subjects with stage IV malignant melanoma, using revised RECIST guideline (version 1.1). Response rate will be computed with associated 95% confidence intervals constructed from the exact Binomial method.

12.2.2 Secondary Endpoints

To characterize safety, tolerability and adverse effects (AE) profile of pembrolizumab followed by HD IL-2 in subjects with stage IV malignant melanoma. Proportion of subjects with each grade of adverse events as defined by CTCAE v4.03 will be computed along with 95% confidence intervals, and reported in a tabular and descriptive manner.

To measure Progression-Free Survival (PFS) using revised RECIST 1.1 after completion of 2 cycles of pembrolizumab and 2 cycles of HD IL-2 in all the subjects enrolled in the study. Median PFS times will be computed if reached, and PFS rates at 1 year +/- 3 months will be calculated with associated 95% confidence intervals based on the Kaplan-Meier method.

To measure overall survival (OS) at 12 months in subjects with stage IV malignant melanoma who showed a response [stable disease (SD), complete response (CR) or partial response (PR)] following completion of 2 cycles of pembrolizumab and 2 cycles of HD IL-2. Median OS times will be computed, and OS rate at 1 year +/- 3 months will be calculated with associated 95% confidence intervals based on the Kaplan-Meier method.

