OBJECTIVES	
Primary Objective Assess the response rate [complete response (CR) + partial response (PR)] of sequential therapy of pembrolizumab followed by high dose IL-2 (HD IL-2) in subjects with stage IV malignant melanoma. Response assessment will be performed using revised RECIST 1.1.
 
Secondary Objectives
 
• Characterize safety, tolerability and adverse effects (AE) profile of pembrolizumab followed by HD IL-2 in subjects with stage IV malignant melanoma.• Measure Progression-Free Survival (PFS) using revised RECIST 1.1 after completion of 2 cycles of pembrolizumab and 2 cycles of HD IL-2 in all the subjects enrolled in the study.• Measure overall survival (OS) at 12 months in subjects with stage IV malignant melanoma who showed a response [stable disease (SD), complete response (CR) or partial response (PR)] following completion of 2 cycles of pembrolizumab and 2 cycles of HD IL-2. 
Exploratory Objectives
 
• Correlate PD-L1 expression in archived diagnostic tumor tissue with best clinical response (revised RECIST criteria) and treatment outcome in subjects with stage IV malignant melanoma.• Correlate Th1/Th2 ratio and myeloid-derived suppressor cells in peripheral blood during therapy with best clinical response (revised RECIST criteria) and treatment outcome in subjects with stage IV malignant melanoma. Data will be collected prior to treatment, during treatment after the 2nd dose of pembrolizumab and after each cycle of HD IL-2.• Correlate the change in soluble PD-L1 and arginine levels in serum/plasma during therapy with best clinical response (revised RECIST criteria) and treatment outcome in subjects with stage IV malignant melanoma. Data will be collected prior to treatment, during treatment after the 2nd dose of pembrolizumab and after each cycle of HD IL-2.• Correlate intestinal microbiome at baseline with best clinical response (revised RECIST criteria) and treatment outcome in subjects with stage IV malignant melanoma.

STUDY DESIGN	Single arm 2-stage Phase II Simon design

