2.1.2 Secondary Objectives

- Characterize safety, tolerability and adverse effect (AE) profile of pembrolizumab followed by HD IL-2 in subjects with stage IV malignant melanoma.
- Measure Progression-Free Survival (PFS) using revised RECIST guideline (version 1.1) after completion of 2 cycles of pembrolizumab and 2 cycles of HD IL-2 in all the subjects enrolled in the study.
- Measure overall survival (OS) at 12 months in subjects with stage IV malignant melanoma who showed a response [stable disease (SD), complete response (CR) or partial response (PR)] following completion of 2 cycles of pembrolizumab and 2 cycles of HD IL-2.

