5.2 HD IL-2 Administration

After completing the 2 cycles of pembrolizumab, High Dose Interleukin-2 (HD IL-2) will be administered. This will require a hospital stay of at least 5 days for each treatment cycle. Established guidelines will be followed for safely administering HD-IL-2 and managing toxicities from this treatment [31,32]. Two treatment cycles will be administered, Cycle 2 being separated from Cycle 1 by approximately 9 days after completion (assuming subject has recovered from Cycle 1 adequately to proceed with Cycle 2). Four weeks after completion of the 2 cycles (called a course of HD IL-2 therapy), disease status will be monitored via CT of the chest and abdomen/pelvis using revised RECIST guidelines (version v1.1, Section 9 of protocol).

Correlative research analyses in this phase include examining the relationship between changes in soluble PD-L1 level and Type 1 T helper cell/Type 2 T helper cell (Th1/Th2) ratios assessed after each of the two HD IL-2 cycles relative to baseline (i.e., pre-dose on Day 1 of Cycle 1 of pembrolizumab treatment), to the best clinical response (modified RECIST criteria) and to treatment outcome.

Drug	Dose	Route	Schedule	Cycle Length
IL-2	600,000 IU/kg ²	Intravenously (IV) over 15 minutes	Every 8 hours for up to 14 doses over 5 days	Days 1-5 = Cycle 1 9 days of rest in between Days 15-19 = Cycle 2

¹ A window of - 1 or + 2 days may be applied to all study visits to accommodate observed holidays, inclement weather, scheduling conflicts etc. Date and time of each drug administration should be clearly documented in subject's chart and electronic case report forms (eCRFs).

²Actual weight will be used unless the patient is 30% over ideal body weight in which case adjusted body weight will be used (Males: IBW = 50 kg + 2.3 kg for each inch over 5 feet.

Females: IBW = 45.5 kg + 2.3 kg for each inch over 5 feet); ABW = IBW + 0.4(actual weight - IBW)

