9.9.7 Progression-Free Survival

A measurement from the date of treatment initiation until the criteria for disease progression is met as defined by RECIST 1.1 or death occurs. Subjects who have not progressed will be right-censored at the date of the last disease evaluation.

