9.9.8 Overall Survival

Overall survival is defined by the date of treatment initiation to date of death from any cause.

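### The only overall survival objective covers subjects with CR, PR or SD after all four cycles, so its 12-month rate sits above the survival of all treated subjects

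*Combined protocol and SAP*

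**What the plan says.** Three places state the OS objective with the same restriction: the synopsis, section 2.1.2 and section 12.2.2. The last limits it to subjects "who showed a response [stable disease (SD), complete response (CR) or partial response (PR)] following completion of 2 cycles of pembrolizumab", with both HD IL-2 cycles required as well. No other OS objective is given.

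Section 9.9.8 sets the time origin: "Overall survival is defined by the date of treatment initiation to date of death from any cause". Section 12.2.2 applies Kaplan-Meier, and section 2.2.2 repeats that analysis without the population: "Median OS times will be computed, and OS rate at 1 year +/- 3 months will be calculated".

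Response status for the subset is settled at restaging after HD IL-2. Section 5.2 says: "Four weeks after completion of the 2 cycles (called a course of HD IL-2 therapy), disease status will be monitored via CT". Section 12.1 agrees, and the study calendar places the CT in the safety visit column, 28 days after the last dose with a tolerance of 7 days. Calendar footnote 5 can be read differently, as Day 19 of the HD IL-2 course plus up to 9 days.

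PFS, by contrast, is to be measured "after completion of 2 cycles of pembrolizumab and 2 cycles of HD IL-2 in all the subjects enrolled in the study", so the OS objective is the narrower of the two.

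**The concern.** Whether a subject belongs to the OS set depends on events after treatment starts: staying alive, completing four cycles and not progressing. Under the protocol therapy discontinuation rules in section 6, documented progression ends protocol therapy, so early progressors cannot complete. Early deaths and subjects who stop for toxicity or by choice drop out too. These groups would be expected to lower the survival curve.

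The result would still appear as the trial's 12-month OS, and section 13.4 requires secondary results to be posted. The OS figures in section 1.2 are not limited to responders or completers. A reader comparing them with this trial would be comparing unlike quantities, and the comparison would favour the new regimen.

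**Working it through.** **The plan's own figure.** There is none for OS: no assumed rate, precision or sample size. The only design calculation is the Simon design for response rate, which has no bearing on OS.

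**Step 1. When membership is known.**
- Pembrolizumab: 2 × 21 = 42 days (section 5.1).
- HD IL-2 course: 19 days (section 5.2).
- Restaging: 28 days later (sections 5.2 and 12.1).
- 42 + 19 + 28 = day 89, and 89 / 30.44 = 2.9 months, or 89 / 365 = 24% of the 12-month window.
- Calendar tolerance of ±7 days: days 82 to 96.
- Footnote 5 read as Day 19 plus up to 9 days: 42 + 19 = day 61, to 61 + 9 = day 70.
- Dose delays make each of these later.

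**Step 2. Direction.** Let S(t) be OS in all treated subjects and L the restaging day. Conditioning on being alive at L gives S(365)/S(L), which cannot be below S(365). Dropping progressors and non-completers raises the rate further, unless those subjects survive as well as or better than the rest.

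**Step 3. Size of the survival condition alone.** As assumed all-treated 12-month rates, take the two pembrolizumab arms of the phase 3 trial in section 1.2: 68.4% and 74.1%. Write H = −ln S(365), which is 0.3798 and 0.2998.
- Constant hazard: rate = exp(−H × (365 − L)/365).
- Hazard before restaging half the later hazard, same S(365): rate = exp(−H × (365 − L)/(0.5L + 365 − L)).

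| L (day) | 68.4%, constant | 68.4%, half early | 74.1%, constant | 74.1%, half early |
|---|---|---|---|---|
| 61 | 72.9% (+4.5) | 70.8% (+2.4) | 77.9% (+3.8) | 76.2% (+2.1) |
| 70 | 73.6% (+5.2) | 71.2% (+2.8) | 78.5% (+4.4) | 76.5% (+2.4) |
| 82 | 74.5% (+6.1) | 71.8% (+3.4) | 79.3% (+5.2) | 77.0% (+2.9) |
| 89 | 75.0% (+6.6) | 72.1% (+3.7) | 79.7% (+5.6) | 77.2% (+3.1) |
| 96 | 75.6% (+7.2) | 72.4% (+4.0) | 80.2% (+6.1) | 77.5% (+3.4) |

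The shift runs from about 2 to about 7 points.

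**Step 4. Adding the exclusion of progressors.** The documents give neither the share with CR/PR/SD nor the survival of the others. As an illustration only, take a constant hazard to day 89. Let q be the share of those alive at day 89 who have CR/PR/SD, and k the later hazard of the others relative to them. Solve S(89) × [q·x + (1 − q)·x^k] = 0.684 for x, the subset's 12-month rate, with S(89) = 0.912. For q from 0.4 to 0.7 and k from 2 to 4, x runs from 79.9% (q = 0.7, k = 2) to 89.8% (q = 0.4, k = 4). Selection on response could therefore be the larger part.

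**Step 5. What a landmark would change.** If no member dies or is censored before L, the first-dose Kaplan-Meier estimate at day 365 is the product of the same terms as a landmark estimate at 365 − L after restaging (276 days for L = 89). With a common restaging day they are identical; with small differences in restaging day they nearly coincide. Only the time axis moves: the median counted from first dose includes 2.0 to 3.2 months (61/30.44 to 96/30.44) in which no member could die.

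**The case against.** The strongest defence is that the restriction is stated openly, so the plan defines a legitimate conditional estimate with no OS hypothesis and no planned comparison. That stands as far as it goes: the figure is not wrong for the subset it describes. It does not answer the complaint that this is the only OS objective and that nothing labels it as conditional on completing treatment without progression.

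A reader might infer that timing from first dose without a landmark is what inflates the 12-month rate. Step 5 shows otherwise: a landmark leaves that rate essentially unchanged. The gap against all treated subjects comes from who is selected.

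A reader might also infer that no OS population is defined. Sections 2.1.2 and 12.2.2 name one. Section 2.2.2 omits it and section 12.4 assigns no analysis set to OS, but section 12.4 assigns none to any endpoint, so the gap is general.

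Two points on size also stand. The base rates come from another trial's patients. Eligibility requires a life expectancy of at least 6 months, which argues against a full constant hazard early on. The half-hazard columns therefore deserve equal weight.

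**Conclusion.** The concern holds as a problem of selection. The reported 12-month OS will lie above that of all treated subjects and should not be presented as the survival of the regimen. The direction follows from the text, given that excluded survivors do no better afterwards than the subset.

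The size is not fixed by the documents. The survival condition alone adds about 2 to 7 points under the assumed base rates, the two hazard shapes and restaging at days 61 to 96. Excluding progressors adds more, by an unknown amount. The median from first dose also carries about 2 to 3 months without possible deaths.

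It would be tempting to extend this to the trial's main conclusion. The documents do not support that: OS is descriptive and secondary, and the response-rate test, the 29 subjects and the stage 1 rule do not depend on it. This should be fixed before analysis.

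**What to change.** - In the synopsis and sections 2.1.2, 2.2.2 and 12.2.2, make the secondary endpoint OS from first dose in all subjects who receive at least one dose (the Safety set of section 12.4), with the Kaplan-Meier rate at 12 months.
- Keep the CR/PR/SD result only as a labelled conditional analysis, with time counted from the post-HD IL-2 restaging. Under one-year follow-up from first dose this leaves about 12.0 − 2.9 = 9.1 months.
- Separately, reconcile the post-HD IL-2 scan timing in calendar footnote 5 with sections 5.2 and 12.1, since it decides when the conditional clock starts.

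The cost is a wording amendment. No extra patients or visits are needed: section 12.1 already follows progressors for OS to one year, and footnote 12 provides long-term follow-up for all subjects, including those who stop treatment for any reason. The downside is a less favourable OS figure and short follow-up for the conditional analysis.
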